#### **6. Procedures Involved**

Chaplains will be asked to volunteer to participate and be consented according to standard IRB-approved protocols. We will enroll a convenience sample of 6-8 chaplains who have already completed the formal CCSH educational course.

[name] (PI) will work with collaborators and CCSH experts to identify the core components of chaplain-delivered CCSH and to develop an objective fidelity-coding manual that we will use to evaluate the fidelity of chaplain-delivered CCSH for patients during HSCT. We will utilize FOI theoretical frameworks to identify structural components (the content that is delivered) and process components (the manner in which chaplains implement content).

1. Chaplains will deliver between four and eight 30-minute sessions (2-4/week) of CCSH to up to 50 adult patients with multiple myeloma or lymphoma during their admission for HSCT. CCSH sessions will be delivered in the patient’s room. The number of sessions between four and eight will be determined based on patient availability, interest, and feasibility. Based on the interviews with staff, we will work within the cancer unit’s workflow to minimize any interference with medical care. Before the chaplain completes each session, we will administer the (<1 min) NCNN Distress Thermometer, a single-item distress thermometer that compares favorably with longer measures used to screen for distress.

2. Chaplains will complete a post-visit fidelity checklist after each session to report which of the key intervention activities were completed.

**Protocol Title: A feasibility study of Chaplain-delivered compassion meditation for patients receiving stem cell transplantation.**

---

3. To rigorously assess fidelity, the study team will collect audio recordings of all CCSH sessions. All sessions will be transcribed verbatim, and two CCSH experts will independently evaluate the extent to which chaplain residents deliver CCSH with fidelity in a random subset of 50% of the sessions. The audio transcripts will be secured on a password-protected Emory server for one year after transcription and will then be destroyed.

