## **7. Study Timelines**

Individual subject participation: approximately 8 months

Chaplain study participants will deliver between four and eight 30-minute sessions (2-4/week) of CSH to 30-50 adult patients with multiple myeloma or lymphoma during their admission for autologous HSCT. We expect recruitment will take up to 8 months.

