## **10. Local Number of Participants**

This is not a multi-site study.

We will enroll a convenience sample of 6-8 chaplains. The 2018 entering class of chaplain residents is 47% male, and 88% non-white. We expect to enroll 50% women, and 50% non-white chaplains.

Chaplains will deliver eight 30-minute sessions (4/week) of CCSH up to 50 adult patients with multiple myeloma or lymphoma during their admission for autologous HSCT. Based on a previous pilot study of yoga with hospitalized HSCT patients, we anticipate that 37% of the patients will be men, and 44% will be non-white.

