### **16. Data Analysis, Management and Confidentiality**

#### **Statistical analysis**

**Measuring and evaluating retention:** Based on a large randomized trial of exercise and stress management programs for patients receiving blood and marrow transplant, we expect that:

- Benchmark 1: 29 (97%) patients enrolled in the study will complete at least one session of chaplain-delivered CSH, based on the fact that 3% of patients enrolled in the larger trial did not receive an intervention).
- Benchmark 2: We will lose 7 patients throughout the trial and thus have complete data from 23 patients (78.8%), based on the Day 100 completion percentage from the trial cited above (78.8%).

We believe this is a conservative estimate because the 78.8% Day 100 completion rate reported in the previous study is approximately 2.5 month past our final time point for this aim.

**Measuring and evaluating adherence:** While chaplains will intend to deliver 8 sessions of CSH during HSCT, we may find that patients are too sick to receive all 8 sessions or that they drop out of the study prior to the completion of all 8. We may also find that chaplains do not deliver the intervention with fidelity during all 8 sessions. Adherence will be evaluated as the percent of sessions completed by patients and characterized as “low” (< 70%), “moderate” (70-80%) and “high” (> 80%) adherence.

- Benchmark 1: We expect that all chaplain residents will achieve high levels of adherence.
- Benchmark 2: We expect that 23 patients will begin the intervention, complete at least one session of CSH and remain in the study until the end of HSCT (see retention benchmarks below), completing at least 75% (6 out of 8) CSH sessions.

**Protocol Title: A feasibility study of Chaplain-delivered compassion meditation for patients receiving stem cell transplantation.**

---

**Data collection:** We will collect audio recordings from all CCSH sessions conducted with enrolled participants. All sessions will be transcribed verbatim, and two CCSH experts will independently evaluate fidelity of implementation (FOI) in a random subset of 50% of the sessions. From the transcripts, coders will quantify 4 dimensions of fidelity according to a recent guide for FOI in meditation studies:

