1) Accuracy (sometimes referred to as *adherence* but called *accuracy* here to avoid confusion with overall adherence): the extent to which the core elements of CCSH were implemented as intended. Accuracy will be evaluated as the percent of session components implemented by chaplains and characterized as “low” (< 70%), “moderate” (70-80%) and “high” (> 80%) accuracy.

2) Dosage: quantified as the amount (percentage) of CBCT that patients receive. We will also characterize the modal number of sessions received as well as the range of sessions completed by all patients. From the range, we will create categories of “low”, “medium”, and “high” dosage that we will use as categorical groups in future studies.

3) Quality: extent to which the chaplain delivered the content as intended. We will generate average competency ratings for each chaplain as well as overall average quality ratings.

4) Responsiveness: the extent to which patients were engaged in each session, operationalized as “maximally,” “moderately”, or “minimally” enthusiastic and attentive during each. We will quantify the average patient engagement for all sessions, as well as the average responsiveness for each session (i.e., 1st – 8th).

In addition, I will quantify Accuracy, Dosage, and Responsiveness from chaplain checklists that chaplains complete after each session.

- Benchmark 1: We will be able to quantify FOI for all chaplain sessions and generate an average FOI for each chaplain
- Benchmark 2: We expect all chaplains will deliver CCSH with high levels of fidelity.

Audio files will be stored for one year after transcription is complete. All other data will be stored for at least 5 years as de-identified data and secured on a password protected Emory server. Only the IRB-approved study team will have access to the data. The PI ([name]) will be responsible for storage and maintenance and destruction of the data.

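### The 50% fidelity-coding sample has no strata and no minimum per chaplain, although the primary endpoint needs a fidelity average for every chaplain

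*Protocol*

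**What the plan says.** Sections 6 and 16 of the protocol both set the expert-coding sample. In the words of Section 16, "two CCSH experts will independently evaluate fidelity of implementation (FOI) in a random subset of 50% of the sessions". Neither section mentions strata, a minimum number per chaplain, or how patients are shared among chaplains.

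Section 16 then lists what the coded sessions must deliver:

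- Quality: "We will generate average competency ratings for each chaplain as well as overall average quality ratings".
- Responsiveness: an overall average, "as well as the average responsiveness for each session (i.e., 1 st – 8 th").
- Benchmarks: the first expects an average fidelity score for each chaplain. The second reads "We expect all chaplains will deliver CCSH with high levels of fidelity".

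Section 4 makes fidelity the primary endpoint. Section 16 also takes Accuracy, Dosage and Responsiveness from a checklist that the chaplain completes after every session. Quality is not among the checklist measures.

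On volume, Section 10 says "We will enroll a convenience sample of 6-8 chaplains" and Section 7 says "Chaplain study participants will deliver between four and eight 30-minute sessions (2-4/week) of CSH to 30-50 adult patients". Section 6 adds: "The number of sessions between four and eight will be determined based on patient availability, interest, and feasibility".

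**The concern.** The sampling rule works on the whole set of sessions, while the results are wanted chaplain by chaplain. A random half of all sessions is not necessarily half of each chaplain's sessions. For a chaplain with many sessions the difference is trivial. For one with few, chance can leave a single coded session, or none.

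Nothing in the protocol prevents a small caseload. The chaplains are 6 to 8 volunteers, patients may have as few as four sessions, and no rule spreads patients among chaplains.

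The second benchmark concerns all chaplains, so it is only as well supported as the least-coded chaplain. If that chaplain has no coded session, there is no Quality average for that person and the benchmark cannot be judged on that dimension. With one coded session, the verdict rests on one conversation with one patient.

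**Working it through.** **Inputs from the protocol.** 50% of sessions coded (Sections 6 and 16); 6 to 8 chaplains (Sections 6 and 10); 30 to 50 patients (Section 7); 4 to 8 sessions per patient (Sections 6 and 7). If every patient has at least 4 sessions, the total T lies between 30 × 4 = 120 and 50 × 8 = 400.

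**The plan's own figures.** The protocol states no number of coded sessions per chaplain. Its nearest figures are the retention benchmarks in Section 16, which imply 30 patients: 0.97 × 30 = 29.1 (stated as 29) and 0.788 × 30 = 23.64 (stated as 23). So 30 patients is the protocol's own lower planning case.

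**Even caseload.** At the lowest volume, 120 / 8 = 15 sessions per chaplain, about 7.5 coded (95% range 4 to 11). The chance that a given chaplain has 0 or 1 coded is 0.0002, so at most 8 × 0.0002 ≈ 0.002 for any of the eight. At the highest volume, 400 / 6 ≈ 67 sessions and about 33 coded; the risk is nil.

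**A chaplain with g sessions.** If T/2 of T sessions are drawn without regard to chaplain, the number coded for a chaplain with g sessions is hypergeometric: P(k) = C(g, k) × C(T − g, T/2 − k) / C(T, T/2). For g = 4 (one patient with four sessions) and T = 180:

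- P(0) = (90 × 89 × 88 × 87) / (180 × 179 × 178 × 177) = 0.060
- P(1) = 4 × 90 × (90 × 89 × 88) / (180 × 179 × 178 × 177) = 0.250
- P(0 or 1) = 0.310

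| Sessions g | P(0 coded) | P(0 or 1 coded) |
|---|---|---|
| 2 | 25% | 75% |
| 3 | 12% | 50% |
| 4 | 6% | 31% |
| 6 | 1.4% | 10.5% |
| 8 | 0.3% | 3% |
| 10 | 0.1% | 1% |

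The table is for T = 180. Moving T from 120 to 400 barely changes it (for g = 4, P(0 or 1) runs from 30.9% to 31.2%). Group size drives the result.

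**How often some chaplain is left thin.** Assume that each patient stays with one chaplain and that 30 patients fall at random, at equal rates, to 8 chaplains. A given chaplain then has exactly one patient with probability 30 × (1/8) × (7/8)^29 = 0.078, and exactly two with probability 435 × (1/8)² × (7/8)^28 = 0.162. At 4 sessions per patient (T = 120), P(0 or 1 coded) is 0.309 with one patient and 0.031 with two. Per chaplain this gives 0.078 × 0.309 + 0.162 × 0.031 ≈ 0.029. Over 8 chaplains the expected number left thin is about 0.23, which agrees with the simulated 22% chance that at least one is.

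Simulation (20,000 runs per case, 30 patients, 8 chaplains), chance that some chaplain who saw a patient has 0 or 1 coded session:

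| Sessions per patient | Equal rates | Uneven rates (assumed) |
|---|---|---|
| 4 | 22% | 36% |
| 6 | 7% | 12–13% |
| 8 | 2% | 4% |

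The chance that some such chaplain has no coded session at all is 4% to 8% in the four-session row. With 6 chaplains and 50 patients at 8 sessions, the chance of 0 or 1 coded stays below 2% even with uneven rates.

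**After drawing within chaplain.** Taking every second session of a chaplain's own list gives at least g/2 rounded down: 2 of 4, and 7 of 15. The chance of 0 or 1 coded is then zero for any chaplain with 4 or more sessions. Chaplains with 1 to 3 need a stated minimum.

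**The case against.** Four points on the other side deserve weight.

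First, a reader might infer that the protocol prescribes a simple random draw from the pooled sessions. It does not say so. The wording would also fit a draw within each chaplain, and operational detail could sit in an analysis plan or in the coding manual still to be written. This stands, and it means that the protocol is not in error. It leaves open a reading that does not secure the averages it asks for.

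Second, the risk depends on small caseloads that the protocol does not predict. Thirty patients over 6 to 8 chaplains is about four or five each, and the 22% applies only if every patient has the minimum of four sessions. Section 16 says that chaplains intend to deliver eight, where the figure is 2% at equal rates. This stands too. If patients were shared between chaplains, the figures would also change.

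Third, the checklists cover every session, so three of the four dimensions exist for every chaplain whatever the draw. That holds, but they are self-report, and Section 6 adds the expert coding for the sake of rigour. Quality is not on the checklist.

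Fourth, every session is recorded and transcribed, so a thin chaplain could be topped up later. That is possible, but a top-up decided after ratings have been seen is weaker than a rule fixed beforehand.

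A reader might also infer that averages for late sessions, session 8 above all, would rest on one or two recordings. Section 16 does warn that "we may find that patients are too sick to receive all 8 sessions or that they drop out of the study", but no figure says how many patients reach session 8. If 20% of 30 do, there are 6 recordings and about an 11% chance of at most one coded; if 10% do, there are 3 and a 50% chance. Both shares are assumptions. Section 16 also expects 23 patients to complete at least 6 of 8 sessions. Averages by session number are asked for only for Responsiveness, which the checklists also give for every session.

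**Conclusion.** The point holds in a limited form. The protocol fixes a 50% random coding sample without strata or a minimum, and asks it to support an average for each chaplain and a benchmark about all chaplains on the primary endpoint. Expert-rated Quality is the most exposed, because it has no second source.

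The size is conditional. It is negligible with an even caseload and matters for chaplains with about 6 sessions or fewer. Under random allocation of 30 patients to 8 chaplains, the chance that at least one is left with 0 or 1 coded session runs from about 2% to 22%, depending on sessions per patient, and higher if caseloads are uneven. These figures assume a pooled draw and one chaplain per patient, neither of which the protocol states.

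The documents do not support the stronger conclusion that the fidelity endpoint cannot be assessed, or that the session-number averages are unsound. This is a cheap safeguard worth adding before coding starts.

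**What to change.** In Sections 6 and 16, state that the random 50% is drawn within each chaplain. One simple way is to sort each chaplain's sessions by session number and take every second one from a random start. Add a minimum of 2 coded sessions per chaplain, or all of them if there are fewer. Report the number of coded sessions beside each chaplain average and each session-number average.

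The cost is small. Rounding adds at most half a session per chaplain, so at most 8 × 0.5 = 4 sessions in all. The minimum adds at most one session over half for a chaplain with 1 to 3 sessions. Fully crossing 8 chaplains with four bands of session number would be dearer: 32 strata, each rounded up by as much as half a session, could add 16 sessions to 90.

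The change secures the chaplain averages. It spreads coding over session numbers but guarantees no particular number at session 8, so no such benefit should be claimed. The text should note that Responsiveness by session number is also available from the self-report checklists for every session.

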## **12. Withdrawal of Participants**

The researchers will stop participation without participant consent if:

- They believe it is in the patient's best interest.
- The patient objects to any future changes that may be made in the study plan.
- The patient is no longer able or willing to receive CCSH.

Participants are free to withdraw from the research at any time. If a participant requests withdrawal, the study team will request permission to use the acquired data and ask the reason for withdrawal.

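### Do the per-session (1st to 8th) Responsiveness averages mislead because different patients stand behind the later sessions?

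*Protocol*

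**What the plan says.** Responsiveness is the fourth of four fidelity dimensions in section 16 of the protocol (Statistical analysis, Data collection). Each session is rated on three ordered levels of patient enthusiasm and attention. The planned summary is: "We will quantify the average patient engagement for all sessions, as well as the average responsiveness for each session", numbered first to eighth.

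Three places make the number of sessions depend on the patient:

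- Section 6: "The number of sessions between four and eight will be determined based on patient availability, interest, and feasibility".
- Section 12 ends participation when "The patient is no longer able or willing to receive CCSH".
- Section 16, on adherence: "we may find that patients are too sick to receive all 8 sessions or that they drop out of the study".

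The same section gives the expected pattern. On retention: "29 (97%) patients enrolled in the study will complete at least one session of chaplain-delivered CSH". On adherence, 23 patients are expected to stay to the end, "completing at least 75% (6 out of 8) CSH sessions". For the ratings, "two CCSH experts will independently evaluate fidelity of implementation (FOI) in a random subset of 50% of the sessions", and as a second source "I will quantify Accuracy, Dosage, and Responsiveness from chaplain checklists that chaplains complete after each session".

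Fidelity of delivery is the primary endpoint (section 4). No benchmark in section 16 refers to a change in Responsiveness from one session to the next.

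**The concern.** Interest is one of the things that sets how many sessions a patient has, and it lies close to what Responsiveness measures. If less engaged patients stop earlier, the averages for later sessions come from a more engaged remainder. The series could then rise with no patient changing, or look flat while engagement fades. If engaged patients leave early for other reasons, such as availability or illness, the series could fall without cause.

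At stake is how the results are read when the programme is refined, which is the secondary objective in section 1. A flat line might be taken as sustained engagement, or a falling line as fatigue with the programme, when part of it is who stayed. The protocol states no other description of engagement over the course.

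**Working it through.** **The plan's own figures.** The benchmarks use an implied base of 30: 0.97 × 30 = 29.1 (stated 29) and 0.788 × 30 = 23.6 (stated 23, which is also 30 − 7, or 76.7%). The share of starters expected to complete at least six sessions is 23/29 = 79%. The plan states no figure for the Responsiveness series, so there is none to reproduce.

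**Assumptions, none of them in the document.** Score 1, 2 or 3, with thirds in each level at session 1 (mean 2.00). Engagement and session count follow a bivariate normal link with correlation ρ, and patients do not change over time. The ratings either carry no within-patient noise, or half of the latent variance is noise (which multiplies ρ by √0.5).

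**Formula.** Let f be the share reaching session 8, z the normal quantile at 1 − f, and c = 0.43 the cut between thirds. Then

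session-8 mean = 1 + P(A > −c | B > z) + P(A > c | B > z),

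where A is the rating scale and B the session-count scale.

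**Results at ρ = 0.3** (first without noise, then with noise):

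| Session counts | f | Without noise | With noise |
|---|---|---|---|
| 4 to 8 equally likely | 0.20 | 1 + 0.811 + 0.495 = 2.31 | 1 + 0.771 + 0.446 = 2.22 |
| 23 of 29 have 6, 7 or 8 equally often | 23/(3 × 29) = 0.26 | 1 + 0.797 + 0.475 = 2.27 | 1 + 0.760 + 0.432 = 2.19 |
| 23 of 29 reach session 8 | 0.79 | 1 + 0.708 + 0.371 = 2.08 | 1 + 0.696 + 0.360 = 2.06 |

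At ρ = −0.3 the shifts are mirrored (1.69, 1.73 and 1.92 without noise). At ρ = 0 there is none.

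**How these cases sit with the protocol.** An even spread over four to eight puts 3/5 = 60% of patients at six or more sessions, below the 79% that section 16 expects. That case is therefore on the pessimistic side. Section 16 also says chaplains intend to deliver eight sessions, which points towards the last row.

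**Masking of a real decline.** Suppose engagement truly falls by 0.48 by session 8. By simulation at ρ = 0.3, the raw change is −0.29 to −0.21 with an even spread over four to eight sessions. It is −0.43 to −0.42 if 23 of 29 reach session 8.

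**Sampling error.** With half of sessions coded by experts and an even spread, session 8 rests on 30 × 0.20 × 0.5 = 3 ratings for 30 patients, or 50 × 0.20 × 0.5 = 5 for 50 patients. By simulation, the standard deviation of the session-8-minus-session-1 difference is 0.54 to 0.56 for 30 patients and 0.40 to 0.43 for 50. The selection shift of 0.22 is about 0.4 of the former (0.22/0.55) and about half of the latter (0.22/0.42). The coded half is drawn at random, so it adds imprecision but not selection.

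**The case for a change.** The strongest case for a change is that the protocol itself fixes the summary by session order. A table laid out that way invites reading across, and one stated driver of session count is close to the quantity being averaged. The remedy would also be cheap. In simulation with 50 patients, four to eight sessions, ρ = 0.3, noise and half of sessions coded, a trend with patient as a fixed effect averaged 0.00 when nothing changed (standard deviation 0.21 to 0.22). The raw difference averaged +0.22. With the true decline of 0.48 the two gave −0.50 and −0.30.

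The mechanism stands, and so does the caution against reading the eight averages as change within patients. What does not follow is that the plan needs changing. It sets no aim about within-patient change in engagement, so the model would answer a question the protocol does not ask. Part of the model's gain in precision comes from assuming a linear course and using all sessions rather than two end points. If patients stop after a poor session, it keeps a small false decline of its own (−0.02 to −0.06 in the simulated cases).

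How many patients stand behind each average, and how sessions are weighted in the overall mean, are matters commonly left to the statistical analysis plan or the report. The planned mode and range of sessions received already show readers that courses differ in length. The chaplain checklist gives a second Responsiveness rating for every session, though it is self-report by the person delivering the session.

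**Conclusion.** No change follows. Carried out as written, the plan yields correct descriptive averages for the sessions delivered, and no benchmark or decision depends on differences between them.

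The possible distortion has no known sign. At an assumed correlation of 0.3 it is 0.06 to 0.08 points on a 1-to-3 scale if 23 of 29 patients reach session 8, and 0.22 to 0.31 if four to eight sessions are equally likely. With noisy ratings, the shift in the even-spread case is smaller than the sampling error of the difference. These figures rest on the assumed scoring, correlation and spread of session counts. A stronger link would make them larger, and no link would make them zero.

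An analyst who presents the series would sensibly print the number of patients and coded sessions beside each average. If change over the course is discussed, the comparison should use the same patients or groups with equal numbers of sessions.

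Separately, section 10 states eight sessions while sections 6 and 7 state four to eight. Those statements must be reconciled, but the conclusion here holds under either, since illness and dropout would still shorten some courses.
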